## **A. SPECIFIC AIMS**

Dental practices have advanced tobacco cessation by adopting a model of brief advice similar to that used by medical providers. We propose a randomized clinical trial designed to allow dental hygienists to provide additional tobacco cessation counseling with little additional marginal effort. This would be done using an internet-based referral to external resources. This system, termed "Refer2Quit", will allow hygienists to refer patients to a patient education website and accompanying Quitline, while the patient is still in the dental office. Our overall goal is to advance science related to internet use in health services delivery by targeting dental hygienists. The intervention will also support subsequent brief counseling by providing feedback on the activities of patients to the practice through a secure server.

We have these specific aims:

- (1) To test the hypothesis that the proportion of patients **REFERRED** to self-management resource websites will be larger in intervention practices compared to control practices. We expect to observe a referral rate of 24% among intervention practices compared to the 12% observed from protocols similar to the control practices.
- (2) To test the hypothesis that the proportion of patients referred who **GO** to the patient self-management website will be larger in intervention practices (40%) compared to control practices (20%).
- (3) To test the hypothesis that the proportion of smokers who are referred who **QUIT** at six months will be larger among intervention (15%) compared to control (10%) because of the additional connectivity of the intervention.

This will be done by randomizing 80 (40 per arm) community-based dental practices into a clinical trial that contrasts the intervention with a paper-based "information prescription".

The intervention is a multi-component internet-delivered clinical microsystem intervention using: (1) "Refer2Quit", a point-of-care "patient referral portal" that hygienists can use to enroll patients into a self-management system; and (2) "Decide2Quit", a patient self-management portal organizing interactive, tailored, patient education and cessation planning links to other high-quality web (smokefree.gov) and offline resources (1-800-QUIT-NOW).

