After initial development, two groups of current smokers were recruited using targeted advertisements on Google (May 2004 and February 2005). Smokers logged onto the website, consented to participate, and completed an introductory questionnaire that resulted in dynamic tailoring of the website. In Phase 1, we assessed usage patterns of 126 smokers. We noted that few participants used the family and doctor info (Table 5). After reviewing these statistics, we added an introductory page to the website with additional content encouraging use of all components. The introductory paragraph included actual data from previous users, encouraged users to use all components of the website, and was signed by the two physicians associated with the study.

Outcomes Assessment - In Phase 2, 212 smokers were randomized to a control website that was linked to other smoking information online (www.smokefree.gov) or to the intervention. Phase 2 trial participants (N = 212) were mostly female (68%), white (80%), and relatively young (63% less than 45). Time spent on the website and use of the family and doctor modules increased, compared with Phase 1 (Table 5).

Phase 2 smokers were then re-contacted by telephone in one month to assess smoking status. Sixty-four participants completed the one month follow-up assessment, and we found no

differences in age, gender, education, or previous quit attempts among those with follow-up and those lost. In intent-to-treat analysis, 9% (9/105) of intervention participants quit smoking compared with 3% (3/107) of the control group (p = 0.069). In an analysis based only on those who completed the follow-up assessment (n=64), a higher percentage of the intervention group reporting quitting (9/31=29%) compared to the control group (3/33=9%, Fisher’s Exact p = 0.055). After adjustment for age, gender, and income, intervention users were still more likely to quit (Odds Ratio = 4.3 (95% CI 1.0 – 20.5)) compared with control. Because users varied in their intensity of using the website, we also looked for a *dose-response* effect. Compared with the control, low-level users (lowest quartile of use) had a small benefit (OR 2.5 (95% CI 0.2-30)), and higher level users were higher (4.44 (CI 1.04-18), p for trend = 0.04).

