We will approach this analysis in two ways. In both approaches, the numerator will be the number of patients who report cessation at six-month follow-up calls. In our primary analysis, we will use an intent-to-treat analysis in that we will include all practices (regardless of whether they actually use the intervention) and will include all smokers who are referred (the same denominator used in H1) regardless of whether they GO to the website. This represents a conservative assessment since we assume that many patients will not GO, and for the purposes of analyses, we will assume that these patients will not have quit. The most conservative analysis would be to use the total number of smokers seen in the practices as the denominator. However, we will not know this number exactly. Our exit cards give an estimate but we do not have a continuous measure of total smokers.

As a secondary analysis, we will assign the denominator as the number of patients who GO to the website. For this secondary analysis, consistent with current guidelines for smoking cessation trials, we will assume that patients who are lost to follow-up, including those who GO and do not agree to follow-up, are smokers.

We have assumed a control cessation rate of 17% among those with completed cases (follow-up complete) in the control group based on a range of completed case and intent-to-treat evaluations of prior internet smoking cessation interventions (Table 11). For the purposes of power calculations, we estimate

**Table 11:** Six-month cessation anticipated among completed cases, those who go to the website, and those referred from 80 practices.

	Six-month cessation among Completed Cases*†		Cessation among those who GO		Cessation among those who are referred‡ (Primary Analysis)	
	n/N	Proportion	n/N	Proportion	n/N	Proportion
Intervention	120/456	26%	120/760	16%	120/1920	6%
Control	20/120	17%	20/200	10%	20/960	2%

\* Completed Cases are those with completed six-month telephone surveys  
 † Assumes 60% follow-up among those who GO (see Table 8 for number who go per practice) and assigns not abstinent to those without follow-up  
 ‡ Assumes those who are referred and do not go are **not abstinent**, based on estimates of those referred from Table 8 multiplied by the number of practices

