a 9% difference in cessation among those with completed cases in the intervention group. Those who do not agree to follow-up will be considered smokers. The intent-to-treat cessation rates are calculated as the sum of the completed case rate (the proportion who quit among those who

complete follow-up), and the rate among those that do not agree to follow-up (assigned as 0% cessation). We conservatively have anticipated that 60% of website participants will agree to follow-up. Thus, we anticipate an intent-to-treat cessation rate among those who go to the website of 15% in the intervention group (See Table 11). Based on this rate we have also calculated the more conservative assessment needed for our primary analysis, assuming that all those patients referred who do not GO are not abstinent.

The prevalence of tobacco cessation will be assessed at six months. Secondary dependent variables for H3 include reports of prolonged cessation, the number of quit attempts, and change in readiness to quit. Models will be constructed treating the number of quit attempts both as a continuous variable and as a Poisson variable. We will conduct additional analyses for quit attempts and change in stage.

Analyses for H3: We will first test the hypothesis for the main outcome (quit rate) and will conduct H3 at the patient level. Because we are comparing rates in all instances between intervention and control practices, we will use a two-group chi-square test of equal proportions to test the statistical difference between the quit rates. Due to the different referral mechanisms and the implications of referral for the providers, we expect that there may be differences in the characteristics of referred smokers between study groups. For instance, it is entirely possible that only those smokers who express a high readiness to change will be referred in the

Principal Investigator/Program Director (Last, First, Middle): DPBRN c/o [name]

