**Hypothesis 2:** This analysis will test the proportion of patients referred who GO to the website, comparing HI-QUIT practices and control practices. As discussed above, a conservative base rate for control practices is for 12% of smokers to be referred and for approximately 20% of those to GO to the website. We expect these proportions to increase for the intervention group to 24% and 40%, respectively. We then need to examine statistical power to detect a 20% difference (40%-20%) in the proportion of referred patients who GO between the two groups, which corresponds to an odds ratio of 2.8. Based on approximately 200 smokers per practice per year and the referral rates above, we expect averages of 24 and 48 smokers to be referred from each control and intervention practice, respectively (Table 8).

Because of the group randomization, our effective sample size must again be reduced by a design factor for each group. Because "GO" to the website is more patient-directed, we have assumed a lower ICC of 0.05 for this analysis. Conservatively assuming an ICC of 0.05, we calculated design factors of 2.2 and 3.6 for the control and intervention groups, respectively. Incorporating the design factors gives an effective sample size per practice of 12 for the control group and 14 for the intervention group. Using a two-sided chi-square test with Type 1 error rate of 0.05, only 10 practices per arm are required to achieve 80% power. If we assume a smaller effect where only 30% of referred smoker in the intervention group GO, 30 intervention practices and 30 control practices are sufficient to achieve 80% power.

**Hypothesis 3:** This analysis of patient cessation outcomes is again conducted at the patient level. As detailed in the analysis plan we will approach this hypothesis in two ways and power calculations will be presented for each. For both approaches, this hypothesis will be tested as a two-sided chi-square test for equality of proportions and the number who quit will be assessed at follow-up among those who visited the website.

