As the primary analysis, and most conservative approach, we will test whether those patients referred through HI-QUIT are more likely to quit than control patients who received information prescription referrals. As in H1), we expect 48 referrals from each intervention practice and 24 from each control practice. Based on ICCs from DTC.Net, we will use an ICC of 0.017 to account for clustering within practices. We further again assume that 20% of referred control patients will GO as will 40% of referred intervention patients. We will

Principal Investigator/Program Director (Last, First, Middle): DPBRN c/o [name]

assume that the cessation rate was 0% among those referred who did not GO. Assuming an intent-to-treat cessation rate of 10% among control patients who GO and 15% for the intervention group (See Table 11), we arrive at overall cessation rates of 2% for the control group and 6% for the intervention group. Only 8 practices per group are required to achieve 80% power to test this hypothesis with a Type 1 error rate of 0.05. If power is reduced by assuming that only 30% of referred intervention group smokers GO, 36 practices per group are required for 80% power.

In summary, evidence suggests that there is ample power to detect clinically significant differences for the three main hypotheses with conservative assumptions.

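### The H3 power statement understates the practices needed: 8 per group gives about 42% power on the protocol's own inputs and about 19 are required, although the planned 30 to 40 per arm still suffice at 2% v 6%

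*Protocol*

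**What the plan says.** Section D10 (Hypothesis 3) says "this hypothesis will be tested as a two-sided chi-square test for equality of proportions". It takes 48 referrals per intervention practice and 24 per control practice, with an ICC of 0.017. It assumes 40% and 20% of those referred GO to the website, that 15% and 10% of those quit, and that nobody else quits: "we arrive at overall cessation rates of 2% for the control group and 6% for the intervention group". It then states "Only 8 practices per group are required to achieve 80% power to test this hypothesis with a Type 1 error rate of 0.05". If only 30% of referred intervention smokers GO, it asks for 36 practices per group. The section closes by calling power ample for all three hypotheses.

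Four related statements bear on this:

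- Section A, Aim 3, says the proportion of referred smokers who quit "at six months will be larger among intervention (15%) compared to control (10%) because of the additional connectivity of the intervention".
- Section D9 defines the primary H3 denominator as "all smokers who are referred (the same denominator used in H1".
- D10 says of the two H3 approaches that "power calculations will be presented for each"; only the analysis of referred patients gets figures.
- D9 says "We conservatively have anticipated that 60% of website participants will agree to follow-up". For the team's own website pilot, section C reports that "Sixty-four participants completed the one month follow-up assessment", out of 212 randomised.

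**The concern.** With 2% v 6% and cluster sizes of 24 and 48, 8 practices contribute only 192 control patients before any allowance for clustering. That is too few for a comparison needing several hundred per group. The figures of 8 and 36 also sit oddly together: lowering the intervention rate from 6% to 4.5% should not multiply the requirement by 4.5 under a single method.

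What is at stake is how much margin a reader believes the cessation hypothesis has. A requirement of 8 against 30 to 40 completing practices suggests a reserve of four- to fivefold; the real reserve is about half that. Aim 3 compounds this by giving the rates for those who GO as if they applied to everyone referred.

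**Working it through.** **Inputs.** From D10: p1 = 0.02, p2 = 0.06, m = 24 (control) and 48 (intervention), ICC r = 0.017, two-sided alpha 0.05. From D10 (Hypothesis 1): design factor D = 1 + (m − 1)r.

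**Trying to reproduce 8.** Equal groups without clustering:
n = [1.96·√(2 × 0.04 × 0.96) + 0.842·√(0.02 × 0.98 + 0.06 × 0.94)]² / 0.04² = 376 per group.
376/48 = 7.8, which rounds up to 8. Two-sided, this needs 48 referrals in both arms and no clustering, contrary to the stated inputs. A one-sided, unpooled, unclustered test at 24/48 also gives 8. Which route was taken cannot be told from the protocol. With r = 0 and the stated 24/48, a two-sided test needs 10 (unpooled) to 13 (pooled) practices.

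**With the stated inputs.**
- D = 1 + 23 × 0.017 = 1.391 (control); 1 + 47 × 0.017 = 1.799 (intervention).
- Effective patients per practice: 24/1.391 = 17.25; 48/1.799 = 26.68.
- Eight practices: n1 = 138.0, n2 = 213.5.
- Pooled rate = (138.0 × 0.02 + 213.5 × 0.06)/351.5 = 0.0443.
- s0 = √[0.0443 × 0.9557 × (1/138.0 + 1/213.5)] = 0.02247.
- s1 = √[0.02 × 0.98/138.0 + 0.06 × 0.94/213.5] = 0.02016.
- Pooled power = Φ[(0.04 − 1.96 × 0.02247)/0.02016] = Φ(−0.20) = 42%.
- Unpooled power = Φ(0.04/0.02016 − 1.96) = Φ(0.02) = 51%.

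A beta-binomial simulation at 8 practices gave 44% (design-effect-adjusted chi-square) and 47% (cluster-level t-test).

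| Scenario (among referred) | Practices for 80%: pooled / arcsine / unpooled | Power at 30 per arm: pooled–unpooled | Power at 40: pooled–unpooled |
|---|---|---|---|
| 2% v 6% | 19 / 17 / 16 | 95–97% | 99% |
| 2% v 4.5% (30% GO) | 39 / 37 / 35 | 69–74% | 81–85% |

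At 2% v 6%, pooled power is 79% at 18 practices and 81% at 19; a continuity correction raises the requirement to 21. Using Table 11's unrounded intervention rate (120/1920 = 6.25%) with control at 2%, pooled power at 8 is 46% and 17 are needed. At 2% v 4.5%, the protocol's 36 practices give 77% (pooled) to 82% (unpooled), so that figure is roughly right with clustering.

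**Aim 3.** Table 8 and D10 attach 15% and 10% to those who GO. Among those referred, 0.40 × 15% = 6% and 0.20 × 10% = 2%, which Table 11 labels the primary analysis.

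**Second H3 approach (denominator: those who GO).** Per practice, 24 × 0.20 = 4.8 and 48 × 0.40 = 19.2. Effective: 4.8/1.0646 = 4.51 and 19.2/1.3094 = 14.66. For 10% v 15%, 30 practices give 135 and 440 effective patients and 30% power pooled (37% unpooled); 40 practices give 180 and 587, and 39% (46%).

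**Follow-up.** The pilot completed 64/212 = 30.2% at one month. Applying 30.2% to D9's completed-case rates of 17% and 26%: 0.20 × 0.17 × 0.302 = 1.0% and 0.40 × 0.26 × 0.302 = 3.1% of those referred. That needs 36 (pooled) or 31 (unpooled) practices per group; pooled power is 72% at 30 and 85% at 40.

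**The case against.** The strongest reply is that the wrong figure decides nothing. Eighty practices are randomised, D5 expects 30 to 40 per arm to complete, and at 2% v 6% these give about 95 to 99% power. That stands. A reader might infer from the error that the trial is underpowered for its primary cessation analysis; on the base assumptions the protocol does not support that.

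A second reply is that D10 counts one year of referrals although access lasts 20 months. If referrals scaled by 20/12 (an assumption: 40 and 80 per practice), 13 to 14 practices would suffice and pooled power for the GO-based analysis at 40 practices would be 57%. This tempers the sizes above, but 13 to 14 is still not 8, and the protocol's own calculation does not use the longer period.

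Three further inferences go beyond the text:

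- The reference to H1's denominator might be read as making all smokers the H3 denominator. The same sentence says smokers who are referred, D9 goes on to explain why total smokers cannot be used, and Tables 10 and 11 use the number referred. Only the cross-reference is wrong; H2 is meant.
- The 60% follow-up might be called a contradiction. D9 and Table 11 both use 60%. The pilot recruited through online advertisements and followed up at one month, so it is an imperfect comparator. It makes 60% look optimistic, not inconsistent.
- Low power for the GO-based analysis might be called a design error. That analysis is explicitly secondary; the defect is that its power was promised and not given.

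**Conclusion.** The statement that 8 practices per group give 80% power for H3 is wrong on its own inputs. Power is about 42% (pooled; 51% unpooled) and about 19 practices are needed (16 to 19 across methods without continuity correction), roughly twice the stated number. The 8 and the 36 do not appear to come from one method.

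The conclusion for the primary H3 analysis at 2% v 6% survives at 30 to 40 practices per arm. The unqualified claim of ample power does not: the 30%-GO scenario has about 69 to 74% at 30 practices, and the GO-based analysis about 30 to 37% at 30 and 39 to 46% at 40, on one-year referrals. Aim 3's 15% v 10% of referred smokers contradicts the 6% v 2% in Table 11 and D10. These results assume ICC 0.017 and the stated cluster sizes. At 0.10, the upper confidence limit for the ICC in section C, 46 to 49 practices per group would be needed for 2% v 6%.

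**What to change.** - In D10, replace 8 with about 19 practices per group and name the method (two-sided chi-square, pooled variance, design factors 1.391 and 1.799). Recompute 36 by the same method (39 pooled).
- State power at 30 and 40 practices per arm for 2% v 6% and for 2% v 4.5%, and qualify the closing claim accordingly.
- Restate Aim 3 as 6% v 2% of referred smokers, equivalent to 15% v 10% of those who GO.
- In D9, change the cross-reference for the H3 denominator from H1 to H2.
- Supply the promised power for the second H3 approach: about 30 to 37% at 30 and 39 to 46% at 40 practices per arm, on one-year referrals.
- Either stop calling 60% follow-up conservative or show sensitivity down to the pilot's 30%.

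The cost is restated text and a short table. The target of 80 practices, the randomisation and data collection do not change.

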## **E. HUMAN SUBJECTS**

This study is pending expedited approval from the Institutional Review Board. In the development phase of our study, we will conduct individual "Think Aloud" usability interviews with local hygienists and patients. These formative data will inform the development of the interactive web-based approach. Written consent will be obtained from each participant. Participants in these formative studies will not be included in the RCT.

The main study will involve recruitment of community-based dental practices in the Dental PBRN to a randomized trial of an Internet-delivered intervention. As discussed above, providers will be contacted by mail with an interest survey, and those interested will be sent additional materials, as discussed above. Providers who agree to participate will agree to: 1) review the contents of a website (intervention or control); 2) allow us to send the follow-up emails with reminders for updates; 3) encourage other hygienists from their practice to participate in the intervention; 4) agree to allow us to recruit patients as they exit their visit to participate in the evaluation using exit card surveys; and 5) allow us to contact a sample of patients participating in websites.

We will recruit patients from the practices to complete exit cards in the waiting rooms after their visit. Exit cards (brief postcard-sized surveys) will be presented to consecutive patients as they leave the office. The exit cards will come with an envelope explaining the study, explaining that participation is voluntary, and that responses will be. Exit cards will be completed anonymously. Participants will seal the exit card in the envelope and place it in the return box before they leave the practice.

For patients referred by hygienists using refer to quit, patient consent is layered and matched to the risk and burden to the patient. Patient consent is not obtained at chairside after they agree to be enrolled. At this level of participation, only patient email is collected. Intervention patients will receive emails after being referred to the intervention website by providers. To minimize risk, the emails will only contain a reminder to go to the website, but will not identify the purpose of the website. No personal health information will be in the emails. Because risk is low and it is not feasible to obtain informed consent without changing the processes of care themselves, we will not obtain informed consent at this level (similar to prior Fax-to-Quit studies).

If patients choose to log onto the web-based system, they will be asked to complete an online consent process where they agree to specific line items (agree to allow us to track their use of the site, agree to follow-up) by online check boxes verified with a username and password they create. If they agree, they will provide telephone numbers for follow-up. If they do not wish to participate in follow-up, they can use the online system without providing additional identifying information. Because participation is again optional, and because requiring written consent would likely greatly decrease use of the online system, we will not obtain written informed consent at this phase. Once the patient is called for follow-up, we will complete a verbal consent procedure for participating in the interview. If the patient reports smoking cessation, we will obtain written informed consent when the specimen is collected. Thus, signature documentation is only obtained for the subset of patients for whom biologic specimens are obtained. This layered procedure has been used in prior studies including DTC.Net and the NCI-funded Smoking Coach study referenced in the application.

A Data Safety and Monitoring Board (DSMB) will be established that includes three individuals, at least two of whom are not associated with UAB. The DSMB will provide reports to the NIDCR and the UAB IRB. The DSMB will meet before the study begins to review the protocol, assess safety, and approve plans for data integrity. For this type of study, evaluating a new type of health care delivery using all approved interventions, there will most likely not be any type of interim data analysis to assess probability of statistically significant group differences. The main purpose of the DSMB will be to monitor success of recruitment, assess data integrity, and monitor for adverse events. Risks to study participants relate mostly to misinterpretation of what

Principal Investigator/Program Director (Last, First, Middle): DPBRN c/o [name]

is research and what is usual care and loss of confidentiality. The DSMB will carefully evaluate how the study is described and that study subjects are informed not to report urgent symptoms through email communications. The DSMB will be convened every six months

